#### **7.1.5. Prohibited Medications**

Participants who are treated with any prohibited medication during the course of the study may require discontinuation. Participants who are administered or take a prohibited medication should be discussed with the sponsor for possible withdrawal from the study.

#### **7.2. Participant Discontinuation/Withdrawal From the Study**

A participant may withdraw from the study at any time at his/her own request. Participants may be withdrawn at the discretion of the investigator. Reasons for discontinuation from the study may include the following: safety, behavioral, compliance or administrative reasons, or if the study is terminated by sponsor.

At the time of discontinuing from the study, if possible, an early discontinuation visit should be conducted. See the [SoA](#) for assessments to be collected at the time of study discontinuation and follow-up and for any further evaluations that need to be completed.

The early discontinuation visit applies only to participants who are enrolled/randomized and then are prematurely withdrawn from the study. Participants should be questioned regarding their reason for withdrawal.

If a participant withdraws from the study, he/she may request destruction of any remaining samples taken and not tested, and the investigator must document any such requests in the site study records and notify the sponsor accordingly.

If the participant withdraws from the study and also withdraws consent (see [Section 7.2.1](#)) for disclosure of future information, no further evaluations should be performed and no additional data should be collected. The sponsor may retain and continue to use any data collected before such withdrawal of consent.

### **7.2.1. Withdrawal of Consent**

Participants who request to discontinue receipt of study intervention will remain in the study and must continue to be followed for protocol-specified follow-up procedures. The only exception to this is when a participant specifically withdraws consent for any further contact with him or her or persons previously authorized by the participant to provide this information. Participants should notify the investigator in writing of the decision to withdraw consent from future follow-up, whenever possible. The withdrawal of consent should be explained in detail in the medical records by the investigator, as to whether the withdrawal is only from further receipt of study intervention or also from study procedures and/or posttreatment study follow-up, and entered on the appropriate CRF page. In the event that vital status (whether the participant is alive or dead) is being measured, publicly available information should be used to determine vital status only as appropriately directed in accordance with local law.

### **7.3. Lost to Follow-Up**

A participant will be considered lost to follow-up if he or she repeatedly fails to return for scheduled visits and is unable to be contacted by the study site.

The following actions must be taken if a participant fails to return to the clinic for a required study visit:

- The site must attempt to contact the participant and reschedule the missed visit as soon as possible. Counsel the participant on the importance of maintaining the assigned visit schedule, and ascertain whether the participant wishes to and/or should continue in the study;
- Before a participant is deemed lost to follow-up, the investigator or designee must make every effort to regain contact with the participant (where possible, 3 telephone calls and, if necessary, a certified letter to the participant's last known mailing address or local equivalent methods). These contact attempts should be documented in the participant's medical record;

- Should the participant continue to be unreachable, he/she will be considered to have withdrawn from the study.

## 8. STUDY ASSESSMENTS AND PROCEDURES

The investigator (or an appropriate delegate at the investigator site) must obtain a signed and dated ICD before performing any study-specific procedures.

Study procedures and their timing are summarized in the [SoA](#). Protocol waivers or exemptions are not allowed.

Safety issues should be discussed with the sponsor immediately upon occurrence or awareness to determine whether the participant should continue or discontinue study intervention.

Adherence to the study design requirements, including those specified in the [SoA](#), is essential and required for study conduct.

All screening evaluations must be completed and reviewed to confirm that potential participants meet all eligibility criteria. The investigator will maintain a screening log to record details of all participants screened and to confirm eligibility or record reasons for screening failure, as applicable.

Participants will be screened within 28 days prior to administration of the study intervention to confirm that they meet the study population criteria for the study. If the time between screening and dosing exceeds 28 days as a result of unexpected delays (eg, delayed drug shipment), then participants do not require rescreening if the laboratory results obtained prior to first dose administration meet eligibility criteria.

A participant who qualified for this protocol but did not enroll from an earlier cohort/group may be used in a subsequent cohort/group without rescreening, provided laboratory results obtained prior to the first dose administration meet eligibility criteria for this study. In addition, other clinical assessments or specimen collections, eg, banked biospecimens, may be used without repeat collection, as appropriate.

Procedures conducted as part of the participant's routine clinical management (eg, laboratory data) and obtained before signing of the ICD may be utilized for screening or baseline purposes provided the procedures met the protocol specified criteria and were performed within the time frame defined in the [SoA](#).

Every effort should be made to ensure that protocol-required tests and procedures are completed as described. However, it is anticipated that from time to time there may be circumstances outside the control of the investigator that may make it unfeasible to perform the test. In these cases, the investigator must take all steps necessary to ensure the safety and well-being of the participant. When a protocol-required test cannot be performed, the investigator will document the reason for the missed test and any corrective and preventive

actions that he or she has taken to ensure that required processes are adhered to as soon as possible. The study team must be informed of these incidents in a timely manner.

All efforts will be made to conduct procedures at the exact nominal time relative to dosing. Procedures up to and including 10 hours after dose administration that are conducted within 10% of the nominal time (eg, within 6 minutes of a 60-minute sample) relative to dosing will not be captured as a protocol deviation, as long as the exact time of the procedure is noted on the source document and data collection tool (eg, CRF/DCT). Procedures scheduled more than 10 hours after dose administration that are conducted  $\leq 1$  hour away from the nominal time relative to dosing will not be captured as a protocol deviation, as long as the exact time of the procedure is noted on the source document and data collection tool (eg, CRF/DCT).

When multiple procedures are scheduled at the same time point(s) relative to dosing, the following chronology of events should be adhered to, where possible:

- ECGs: obtain prior to vital sign measurements and as close as possible to the scheduled time, but prior to blood specimen collection (see [Section 8.2.3](#));
- Vital Signs (BP and pulse rate): obtain as close as possible to the scheduled time, but prior to blood specimen collection (see [Section 8.2.2](#));
- Weight: obtain as close as possible to the scheduled time, but prior to eating and drinking and prior to dose administration, where applicable (see [Section 8.9.3](#));
- Fasting blood samples: after assessment of 12-lead ECG and vital signs but prior to dosing;
- PK blood specimens: obtain at the scheduled time (for 0H samples, collect before dosing and as close as possible to dosing time, where applicable);
- Dosing: must occur at the scheduled nominal time and following predose blood sample collection;
- Breakfast: provided for consumption following dosing, where applicable (see [Section 5.3.1](#)).

Safety/laboratory/analyte results obtained following 1st dose of the study intervention (Day 1) that could unblind the study (ie, glucose, insulin, glucagon, C-peptide, HbA1c, and PK), will not be reported to investigative sites or other blinded personnel until the study has been unblinded.

If an IV catheter is utilized for blood sample collections, ECGs and vital sign assessments (pulse rate and BP) should be collected prior to the insertion of the catheter.

For samples being collected and shipped, detailed collection, processing, storage, and shipment instructions and contact information will be provided to the investigator site prior to initiation of the study.

The total blood sampling volume for individual participants is approximately, *up to* 425 mL. If participants with obesity are enrolled, approximately, *up to* 245 mL blood will be collected. The actual collection times of blood sampling may change. Additional blood samples may be taken for safety assessments at times specified by Pfizer, provided the total volume taken during the study does not exceed 550 mL during any period of 56 consecutive days.

### **8.1. Efficacy Assessments**

Not applicable.

### **8.2. Safety Assessments**

Planned time points for all safety assessments are provided in the [SoA](#). Unscheduled clinical laboratory measurements may be obtained at any time during the study to assess any perceived safety issues.

#### **8.2.1. Physical Examinations**

A complete physical examination will include, at a minimum, head, ears, eyes, nose, mouth, skin, heart and lung examinations, lymph nodes, and gastrointestinal, musculoskeletal, and neurological systems.

A brief physical examination will include, at a minimum, assessments of general appearance, the respiratory and cardiovascular systems, and participant-reported symptoms.

Physical examinations may be conducted by a physician, trained physician's assistant, or nurse practitioner as acceptable according to local regulation.

Height will also be measured and recorded per the [SoA](#).

Physical examination findings collected during the study will be considered source data and will not be required to be reported, unless otherwise noted. Any untoward physical examination findings that are identified during the active collection period and meet the definition of an AE or SAE ([Appendix 3](#)) must be reported according to the processes in [Sections 8.3.1 to 8.3.3](#).

#### **8.2.2. Vital Signs**

Supine BP will be measured with the participant's arm supported at the level of the heart, and recorded to the nearest mm Hg after approximately 5 minutes of rest. The same arm (preferably the dominant arm) will be used throughout the study. Participants should be instructed not to speak during measurements. When triplicate measurements are obtained, they should be collected approximately 2 minutes apart; the average of the triplicate measurements at each nominal time point on Day -1 will serve as each participant's time-controlled baseline value.

The same properly sized and calibrated BP cuff will be used to measure BP each time. The use of an automated device for measuring BP and pulse rate is acceptable; however, when

done manually, pulse rate will be measured in the brachial/radial artery for at least 30 seconds. When the timing of these measurements coincides with a blood collection, BP and pulse rate should be obtained prior to the nominal time of the blood collection.

Additional collection times, or changes to collection times, of BP and pulse rate will be permitted, as necessary, to ensure appropriate collection of safety data.

### 8.2.3. Electrocardiograms

Standard 12-lead ECGs utilizing limb leads (with a 10 second rhythm strip) should be collected at times specified in the [SoA](#) section of this protocol using an ECG machine that automatically calculates the heart rate and measures PR, QT, and QTc intervals and QRS complex. Alternative lead placement methodology using torso leads (eg, Mason-Likar) should not be used given the potential risk of discrepancies with ECGs acquired using standard limb lead placement. All scheduled ECGs should be performed after the participant has rested quietly for at least 5 minutes in a supine position. When a meal or snack is scheduled at the same time as an ECG, the ECG measurement must be performed prior to the meal/snack.

Triplicate 12-lead ECGs will be obtained approximately 3 minutes ( $\pm 1$  minute) apart; the average of the triplicate ECG measurements collected at each nominal time point on Day -1 will serve as each participant's time-controlled baseline value. Any clinically significant changes from the baseline/Day 1 ECG may potentially be AEs ([Appendix 7](#)) and should be evaluated further, as clinically warranted. To ensure safety of the participants, a qualified individual at the investigator site will make comparisons to baseline measurements. Additional ECG monitoring will occur if a) the mean value from the triplicate measurements for any postdose QTcF interval is increased by  $\geq 60$  msec from the baseline **and** is  $> 450$  msec; or b) an absolute QT value is  $\geq 500$  msec for any scheduled ECG. If either of these conditions occurs, then a single ECG measurement must be repeated at least hourly until QTc values from 2 successive ECGs fall below the threshold value that triggered the repeat measurement.

If a) a postdose QTcF interval remains  $\geq 60$  msec from the baseline **and** is  $> 450$  msec; or b) an absolute QT value is  $\geq 500$  msec for any scheduled ECG for greater than 4 hours (or sooner, at the discretion of the investigator); or c) QTcF intervals get progressively longer, the participant should undergo continuous ECG monitoring. A cardiologist should be consulted if QTcF intervals do not return to less than the criteria listed above after 8 hours of monitoring (or sooner, at the discretion of the investigator).

In some cases, it may be appropriate to repeat abnormal ECGs to rule out improper lead placement as contributing to the ECG abnormality. It is important that leads be placed in the same positions each time in order to achieve precise ECG recordings. If a machine-read QTc value is prolonged, as defined above, repeat measurements may not be necessary if a qualified medical provider's interpretation determines that the QTcF values are in the acceptable range.

ECG values of potential clinical concern are listed in [Appendix 7](#).

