### 7.1.1. ECG Changes

A participant who meets either bulleted criterion based on the average of triplicate ECG readings will be withdrawn from the study intervention.

- QTcF >500 msec.
- Change from baseline: QTcF >60 msec and QTcF > 450 msec.

If a clinically significant finding is identified (including, but not limited to, changes from baseline in QTcF after enrollment), the investigator or qualified designee will determine if the participant can continue in the study and if any change in participant management is needed. This review of the ECG printed at the time of collection must be documented. Any new clinically relevant finding should be reported as an AE.

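### In Protocol 8.2.3 the absolute trigger for repeat ECGs and continuous monitoring is uncorrected QT only, so a narrow group stopped under 7.1.1 for mean QTcF >500 msec does not trigger mandatory hourly ECGs.

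*Protocol*

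**What the plan says.** **Stopping rule (Protocol 7.1.1).** A participant meeting either of two criteria "based on the average of triplicate ECG readings will be withdrawn from the study intervention". The first criterion is "QTcF >500 msec". The second is a rise in QTcF of more than 60 msec from baseline together with QTcF above 450 msec.

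**Repeat-ECG rule (Protocol 8.2.3).** Limb (a) is a mean triplicate QTcF that has risen by at least 60 msec and is above 450 msec. Limb (b) begins "an absolute QT value is" and sets the level at 500 msec or more, "for any scheduled ECG. If either of these conditions occurs, then" the repeats follow: "a single ECG measurement must be repeated at least hourly until QTc values from 2 successive ECGs fall below the threshold value that triggered" them.

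**Continuous-monitoring rule (Protocol 8.2.3, next paragraph).** Limbs (a) and (b) return as persistence conditions, with limb (b) again in uncorrected QT. Limb (c) is progressive lengthening of QTcF.

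**Baseline.** In Protocol 8.2.3, "the average of the triplicate ECG measurements collected at each nominal time point on Day -1 will serve as each" participant's time-matched baseline.

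**Surrounding sentences.** The cardiology sentence is in QTcF: "A cardiologist should be consulted if QTcF intervals do not return to less than the criteria listed above after 8 hours of monitoring". A later sentence allows a waiver: "If a machine-read QTc value is prolonged, as defined above, repeat measurements may not be necessary if a qualified medical" provider judges the QTcF values acceptable.

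**The concern.** The two sections use different measures for the same 500 msec level. Limb (a) is in QTcF and always covers the second stopping criterion. The first criterion, an absolute QTcF above 500, is covered only when the rise is at least 60 msec or when uncorrected QT also reaches 500. At heart rates above 60 bpm, QT is shorter than QTcF, so limb (b) can stay silent while QTcF is over 500. Protocol 2.2.2.1 reports a trend toward modest heart-rate increases in blinded data from the ongoing multiple-dose study, and that direction makes limb (b) less sensitive.

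At stake is monitoring of a participant who has just met the absolute stopping level. Protocol 7.1 keeps that participant in the study for safety evaluation where possible. Table 2 schedules ECGs on Days 1 and 42 at 0, 1, 2, 4, 8, 12 and 24 h, so successive gaps are 1, 1, 2, 4, 4 and 12 h. The schedule therefore does not stand in for an hourly repeat.

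**Working it through.** The documents give no figure to reproduce here. The check codes the written thresholds as logical rules and looks for cases that meet 7.1.1 but neither limb of 8.2.3.

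**Inputs**
- Stop dosing: mean QTcF >500, or rise >60 with QTcF >450 (Protocol 7.1.1).
- Limb (a): rise ≥60 with QTcF >450. Limb (b): QT ≥500 (Protocol 8.2.3).
- Fridericia: QTcF = QT/RR^(1/3) with RR = 60/HR (SAP 3.1.4), so QT = QTcF × (60/HR)^(1/3).
- Screening QTcF limit: 450 msec (Protocol 5.2, exclusion 17).

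**Step 1: conditions for a gap.** Three things must hold together: QTcF >500; rise <60, so baseline >440; and QT <500. The last requires HR > 60 × (QTcF/500)^3:

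| Mean QTcF (msec) | QT is below 500 when HR exceeds |
|---|---|
| 501 | 60.4 bpm |
| 505 | 61.8 bpm |
| 509 | 63.3 bpm |

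**Step 2: single cases**

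| Baseline | QTcF | HR | Rise | QT | Must stop? | Limb met |
|---|---|---|---|---|---|---|
| 445 | 501 | 80 | 56 | 455.2 | yes | none |
| 445 | 502 | 75 | 57 | 466.0 | yes | none |
| 450 | 509 | 64 | 59 | 498.2 | yes | none |
| 450 | 509 | 63 | 59 | 500.8 | yes | (b) |
| 445 | 502 | 60 | 57 | 502.0 | yes | (b) |
| 440 | 501 | 75 | 61 | 465.1 | yes | (a) |

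**Step 3: grid.** Whole-msec baseline 360-450 and QTcF 400-560, with HR 45-110 in steps of 1 bpm and the three readings of a triplicate taken as equal. Cells are unweighted and are not probabilities.
- As written: 2,211 cells meeting the first stopping criterion escape both limbs, all at baseline 442-450, QTcF 501-509 and HR ≥61. No cell meeting the second criterion escapes.
- Adding QTcF ≥500 to limb (b): 0 escapes, 0 triggers lost, and 2,711 cells gain a trigger (the 2,211 plus 500 at QTcF exactly 500).
- Replacing QT by QTcF: 0 escapes, but 9,006 cells lose a trigger, 4,368 of them with QTcF >480.

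**Step 4: sensitivity**
- *Per-tracing reading of limb (b).* If one tracing lies d msec above the mean QT, the cutoff becomes HR > 60 × (QTcF/(500 − d))^3. At QTcF 501 this is 62.2 bpm for d = 5 and 64.1 bpm for d = 10 (d is assumed). In the first case of Step 2, a tracing would have to be 500 − 455.2 = 44.8 msec above the mean to fire limb (b).
- *Baseline above 450.* The 450 limit applies at screening, whereas baseline is Day -1. A Day -1 baseline of up to 460 or 470 (assumed) extends the window to QTcF 519 or 529. The added QTcF condition again leaves 0 escapes and loses no trigger.

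**The case against.** **Intent.** The strongest reply is that this is a wording slip. The exit test, the cardiology sentence and the waiver sentence are all in corrected QT, so a sensible site would probably read limb (b) as QTc. That is likely the intent, but Protocol 8 calls adherence to the design requirements essential and allows no waivers, and the text of limb (b) says QT in both paragraphs.

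**Other safeguards.** Dosing stops under 7.1.1. For a clinically significant finding, that section also has the investigator decide on management and document the ECG review. Appendix 7 lists QTcF above 500 as a possible SAE. Protocol 8 asks for immediate discussion of safety issues with the sponsor. Limb (c) can lead to continuous monitoring, and participants are inpatients through the dosing period. All of this stands and limits the consequence: a site would hardly wait 4 or 12 h for the next scheduled tracing. None of it, however, makes hourly repeats mandatory for this group.

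**A stronger reading: the exit rule is also wrong.** A reader might infer this because a QT trigger is cleared by QTc values. At 50 bpm, for example, QT 500 is QTcF 470.5, so repeats could end while QT is still 500. The documents do not support calling that an error. Ending repeats once the rate-corrected value is below the threshold is a defensible use of rate correction, and the waiver sentence points the same way. Requiring QT itself to fall could hold a participant with a slow heart rate on hourly ECGs although QTcF was never near 500.

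**Per-tracing QTcF.** Adding QTcF on any single tracing would be too wide. Section 7.1.1 uses the triplicate average, and Protocol 9.3.2.1 has a lone tracing above 500 described in context but not counted in the categorical analysis. This objection is accepted, and the fix uses the mean.

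**Conclusion.** The gap is real on the text. Limb (b) of both rules in Protocol 8.2.3 omits corrected QT. A participant stopped solely for mean QTcF above 500, with a rise below 60 and QT below 500, meets neither limb for hourly repeats and neither limb (a) nor (b) for continuous monitoring.

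It is small. The 442-450 baseline and 501-509 QTcF window rests on a baseline no higher than the screening limit, and the heart-rate cutoff of about 60-63 bpm rests on Fridericia's formula with limb (b) applied to the mean. The documents give no QTcF distribution, so no expected count can be stated. With 3 × 9 = 27 active participants planned, few or none may be affected.

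A reader might infer that participants with QTcF above 500 would continue dosing or go unmonitored, or that the primary safety analysis is compromised. The documents do not support either: 7.1.1 stops dosing, the other safeguards apply, and no endpoint or estimate changes. This is a minor correction to a safety rule, worth making because it costs so little.

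**What to change.** In both paragraphs of Protocol 8.2.3, keep the existing QT condition in limb (b) and add: *or the mean triplicate QTcF is ≥500 msec (the single reading where only one ECG is taken)*. The triplicate mean matches 7.1.1. The single-reading clause covers the follow-up and early-termination visits, where Table 1 schedules one ECG.

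Leave the exit rule alone, since its QTc wording already fits a QTcF trigger. The addition also gives the cardiology sentence a QTcF 500 criterion to refer back to.

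Do not replace QT with QTcF. At 55 bpm, QT 500 is QTcF 485.7, above the 480 level in Appendix 7, and that existing trigger would be lost. That Appendix 7 level marks a possible AE and is not itself a repeat-ECG trigger, but a correction meant to close a gap should not remove monitoring.

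The cost is one added clause in each of two sentences and a few extra repeat ECGs, which the existing waiver can limit on a qualified provider's reading. Section 7.1.1, Appendix 7 and the SAP need no change.
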